5.6.4 Incomplete date for anti-neoplastic therapies

Prior therapies

Start date:

The same rule which is applied to the imputation of AE/concomitant medication start date will be used with the exception that for scenario (B) will be replaced to be 'start date of study drug -1'.

End date:

Imputed date = min (start date of study drug, last day of the month), if day is missing;

Imputed date = min (start date of study drug, 31DEC), if month and day are missing.

If the end date is not missing and the imputed start date is after the end date, use the end date as the imputed start date.

If both the start date and the end date are imputed and if the imputed start date is after the imputed end date, use the imputed end date as the imputation for the start date.

Post therapies

Start date:

Imputed date = max (last date of study drug + 1, first day of the month), if day is missing;

Imputed date = max (last date of study drug + 1, 01JAN), if day and month are missing.

End date: No imputation.

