#### **7.1.3 End of treatment visit**

At any time, patients may voluntarily withdraw from the study or be removed from it at the discretion of the investigator. If withdrawal occurs, or if the patient fails to return for visits, effectively withdrawing, the investigator should make a reasonable effort (e.g. telephone, e-mail, letter) to understand the primary reason for a patient's premature withdrawal, record this information on the End of Treatment eCRF, and notify Novartis. Patients may be withdrawn from LDK378 for one of the following reasons:

1. Adverse event(s).
2. Disease progression.
3. Protocol violation/deviation.

4. Patient withdrew consent.
5. Lost to follow-up.
6. Death.

Patients who discontinue LDK378 for any of the above reasons (except death) should be scheduled for an end of treatment (EOT) visit 14 days (up to 21 days) after discontinuing LDK378, at which time all of the assessments listed for the EOT visit will be performed. An EOT eCRF will be completed, giving the date and reason for stopping the LDK378.

The EOT completion evaluations include the following:

- A physical examination, including an assessment of any tumor lesions; Karnofsky/Lansky performance status; height/weight and vital signs; hematology; chemistry; pregnancy test for FCBP.
- Radiological tumor evaluation of all tumor sites, if not evaluated  $\leq 28$  days prior to the EOT visit, and if objective evidence of disease progression has not previously been documented.
- For neuroblastoma patients: MIBG imaging, if positive at baseline and not evaluated  $\leq 28$  days prior to the EOT visit.
- For neuroblastoma and lymphoma patients: If bone marrow bilateral aspirate and biopsies were performed and were positive at screening, it will be left to the investigator's discretion to monitor the bone marrow aspirate at each disease evaluation. In order to confirm a Complete disease Response (CR), bone marrow biopsy or aspirate may be required when a radiological CR has been achieved.
- ECG.
- Occurrence of new AEs and status of current AEs.
- Collection of a fresh tumor biopsy, if medically feasible, and the patient and/or guardian agrees.

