## **10.5 Handling of missing values/censoring/discontinuations**

Patients in the dose-escalation part who are ineligible for the dose-determining set may be replaced if necessary. Patients in the safety expansion part will not be replaced.

As of the date of data-cutoff for the final CSR for the purposes of reporting:

- Time to event data (i.e. PFS) will be censored if no event is observed before the cut-off date or before the start date of a new anti-neoplastic therapy, whichever occurs earlier. The censoring date will be the date of last adequate tumor assessment before either of these two dates. If a PFS event is documented after two or more missing or non-adequate tumor assessments, then the date of PFS will be censored at the date of the last adequate tumor assessment. If a PFS event is observed after a single missing or non-adequate tumor assessment, the actual date of event will be used.
- Continuing events (e.g. adverse events, concomitant therapies, etc.) will be summarized using the data cut-off date as the date of completion, with an indication within listings that the event is continuing.

For patients who discontinue the study with ongoing events, the discontinuation date will be used as the completion date of the event with the appropriate censoring as described in the above paragraph.

The reason for discontinuation from study will be summarized and listed, along with dates of first and last LDK378, duration of exposure to LDK378 and date of discontinuation for each patient.

Other missing data will simply be noted as missing in appropriate tables/listings. The FAS will be used.

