If the observed ORR is equal to or greater than 30%, then this will be considered as preliminary evidence of substantial antitumor activity of LDK378 in ALK activated neuroblastoma. If the observed ORR is between 20% and 30% then this will be considered as evidence of moderate antitumor activity, and as limited antitumor activity if it is between 10% and 20%. If the observed ORR is less than 10% (i.e. ≤ 2 CR or PR out of 25), then insufficient antitumor activity will be declared.

Note that for a sample size of $n = 25$ (see section 10.8), if the observed ORR is greater than or equal to 20% (i.e. ≥ 5 CR or PR), then the true ORR has a posterior risk of less than 10% of being in the insufficient antitumor activity category.

A minimally informative unimodal Beta prior distribution of the true ORR is derived as follows. A priori it is assumed that the true mean of the ORR equals 20%. A true ORR of 20% is the midpoint between limited and moderate antitumor activity and serves as a compromise between a skeptical view assuming the treatment has only limited antitumor activity and an optimistic view assuming the treatment has moderate antitumor activity. The parameters of the minimally informative Beta prior distribution of the ORR are then derived as $a=1/4$ and $b=1$.

Best Overall Response

Best overall response (BOR) is the best response recorded from the start of the treatment until disease progression. Patients with a BOR of 'UNKNOWN' will be treated as non-responders when estimating ORR. If any non-palliative cancer therapy is taken while on study any subsequent assessments will be excluded from the BOR determination. MIBG response score per curie criteria will be recorded and listed for patients with neuroblastoma who had MIBG scan.

Determination of BOR per RECIST 1.1

ORR is defined as the proportion of patients with a best overall complete response (CR) or partial response (PR) per RECIST 1.1.

For patients with the primary diagnosis other than lymphoma, BOR will be based on the overall lesion assessment per RECIST 1.1. The evaluation of overall lesion response at each assessment is a composite of the target lesion response, non-target lesion response and presence of new lesions (for details see Protocol Appendix 5).

The BOR for each patient is determined from the sequence of overall (lesion) responses according to the following rules:

- CR = at least two determinations of CR at least 4 weeks apart before progression

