2.7 Analysis of other secondary efficacy objectives

Progression-free survival

PFS is defined as the time from the start date of study drug to the date of the first radiologically documented PD or death due to any cause per RECIST 1.1, for patients with solid tumor; and from the start date of study drug to the date of the first PD as overall disease response or death due to any cause per Cheson, for patients with lymphoma.

If a patient has not progressed or is not known to have died at the date of analysis cut-off or has received any further anticancer therapy, PFS will be censored at the date of the last adequate tumor evaluation before the cut-off date or before the start of the new anticancer therapy date, whichever is earlier. Clinical deterioration will not be considered as a qualifying event for progression.

In particular, PFS will be censored at the last adequate tumor assessment if one of the following occurs:

- 1: Ongoing without event
- 2: Lost to follow-up

- 3: Withdrew consent
- 4: Adequate assessment no longer available
- 5: Initiation of new cancer therapy prior to progression
- 6: Event after ≥ 2 missing tumor assessments

PFS will be described in tabular and graphical format for patients treated at MTD/RDE by expansion (disease) group, and also by indication and by treatment group using Kaplan-Meier methods as described for DOR, including estimated median (in months) with 95% CI, 25th and 75th percentiles and Kaplan-Meier estimated probabilities with corresponding 95% CIs at several time points (including at least 2, 4, 6, 8, 10, 14 months). Censoring reasons will also be summarized. Also duration between treatment start date and cut-off date, and PFS follow-up time will be summarized by expansion, and also by indication and by treatment group.

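### SAP 5.6.4 sets a partly dated post-study therapy to its earliest possible day without checking it against documented progression, so a PFS or DOR event found after the last dose can become a censored time

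*SAP*

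**What the plan says.** **Imputation.** For post-study therapies, SAP 5.6.4 gives two start-date rules. With the day missing: "Imputed date = max (last date of study drug + 1, first day of the month), if day is missing". With day and month missing: "Imputed date = max (last date of study drug + 1, 01JAN), if day and month are missing". Neither mentions progression. Under prior therapies the same section does contain a consistency check ("If the end date is not missing and the imputed start date is after the end date, use the end date as the imputed start"), but the post-therapy rules have none.

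**Use of the therapy date.** SAP 2.7 censors PFS at the last adequate tumor evaluation before the analysis cut-off "or before the start of the new anticancer therapy date, whichever is earlier", and lists as a censoring reason "5: Initiation of new cancer therapy prior to progression". Protocol 10.5 agrees: PFS is censored if no event is seen before the cut-off or "before the start date of a new anti-neoplastic therapy, whichever occurs earlier". Protocol Appendix 5, Table 3-2, situation F has the same default and also covers duration of response. SAP 5.4.1 counts medication, surgery and radiotherapy as new cancer therapy.

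**When PD can be found after the last dose.** Under Protocol 7.1.3, patients who stop "should be scheduled for an end of treatment (EOT) visit 14 days (up to 21 days) after discontinuing LDK378", with a tumor scan if none was done in the preceding 28 days and PD is not yet documented. Protocol 2.6 instead places this visit within 7 days of the last dose. The two passages need reconciling, but the result below is the same for either. Later therapies are collected at the follow-up contact 30 (up to 37) days after LDK378 stops.

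**The concern.** Whether a patient counts as an event or as censored depends on the order of two dates, and one of them may be imputed. For a PD that lies inside the interval left open by the partial date, the rule puts therapy first, although the usual sequence is a scan showing PD followed by a change of treatment.

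The exposed patients are foreseeable. SAP 2.7 and 5.4.1 do not accept clinical deterioration as progression, so for a child taken off drug on clinical grounds the end-of-treatment scan may be the only route to a PD event. If that event is lost, the patient is censored at the last adequate assessment, or at treatment start if there was none. The censoring is informative, because the patient is known to have progressed.

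**Working it through.** The documents state no figure that depends on this rule, so there is nothing to reproduce.

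**1. The rule applied to dated examples (day missing).** Imputed start = max(last dose + 1, first of recorded month).

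| Last dose | PD | True therapy start | Imputed start | Outcome |
|---|---|---|---|---|
| 06 Mar | 20 Mar | 27 Mar | 07 Mar | PD replaced by censoring |
| 24 Mar | 07 Apr | 14 Apr | 01 Apr | PD replaced by censoring |
| 15 Mar | 29 Mar | 05 Apr | 01 Apr | PD kept |
| 20 Mar | 20 Mar | 27 Mar | 21 Mar | PD kept |
| 20 Mar | 13 Mar | 27 Mar | 21 Mar | PD kept |

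Row 3 is safe because the PD falls in an earlier month than the therapy. Rows 4 and 5 are safe because of the last dose + 1 term.

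**2. Share of PDs lost.** Condition on a PD after the last dose, therapy truly starting g days after the PD, and a missing day. The PD is on or after the imputed start exactly when PD and therapy fall in the same calendar month. With last-dose days spread evenly over the year, that share is about 1 - g/30.4:

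- g = 7: 1 - 7/30.4 = 0.77
- g = 14: 1 - 14/30.4 = 0.54
- g = 16: 1 - 16/30.4 = 0.47

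Counting over all 365 last-dose days gives the same values, and they do not change when the PD lies 1, 7, 14 or 21 days after the last dose. If a PD on the imputed day itself is kept, a PD on the 1st of the month is spared, which removes about 1/30.4 = 0.03. Averaging over a range of gaps:

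- therapy 1-7 days after PD (mean 4): 1 - 5/30.4 = 0.84
- therapy 1-14 days after PD (mean 7.5): 1 - 8.5/30.4 = 0.72
- therapy 7-21 days after PD (mean 14): 1 - 15/30.4 = 0.51

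A simulation of 40,000 draws per scenario, with the scan 14-21 days after the last dose, gave 0.836, 0.720 and 0.512.

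**3. Direction of the bias.** Take one PD moved back to a censoring time with n patients then at risk, no ties and no other censoring in between. The Kaplan-Meier curve after the PD time is multiplied by n/(n - 1). With ten events at times 1 to 10, moving the event at 6 to censoring at 3.5 (n = 7) changes S(6) from 0.400 to 0.400 x 7/6 = 0.467. Between the two times the curve can dip slightly: S(4) goes from 0.600 to 0.583.

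**4. Illustrative size.** Assumed, because the documents do not give them: exponential PFS with a true median of 8 or 24 weeks, and the number of PDs switched. Scans follow Day 15 of cycles 2, 4, 6, 10, 14, 20 and 26 (weeks 5, 11, 17, 29, 41, 59, 77). There were 2,000 runs per setting.

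| N | True median (wk) | PDs switched | Mean KM median (wk), before to after |
|---|---|---|---|
| 25 | 24 | 1 | 28.4 to 29.7 |
| 25 | 24 | 4 | 28.5 to 33.6 |
| 25 | 8 | 1 | 10.6 to 10.8 |
| 25 | 8 | 4 | 10.5 to 11.7 |
| 83 | 24 | 2 | 28.3 to 28.8 |
| 83 | 24 | 10 | 28.2 to 31.2 |

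For N = 25 and a 24-week median, 26-week PFS moved from 55.3% to 56.6% with one switched PD, and from 55.0% to 60.7% with four. The share of runs in which the median fell rounded to zero in every setting.

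**The case against.** The strongest reply is that several conditions must coincide: PD first documented after the last dose, a partial therapy date, an imputed date that precedes the PD, and therapy that truly began after the PD. Where therapy really came first, censoring is what the plan intends. Therapy is collected at 30-37 days and missing values are queried (Protocol 9.4), so partial dates should be few. SAP 5.6.4 also does not name PFS or DOR; the link is inferred because no other rule for partial therapy dates is given. Censoring reasons are summarized and post-study therapies listed, so cases could be traced. All of this stands. It limits the size but does not remove the defect in the rule.

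A reader might infer more than the documents support:

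- *That every PD after the last dose is lost.* A PD in a month before the recorded therapy month is kept.
- *That records with only the year matter most.* Nearly all exposed PDs would be lost there (96-100%), but a year-only date for a therapy recorded about five weeks after the last dose is unlikely.
- *That the event time always moves back by a full scan interval.* The end-of-treatment scan needs only a gap of more than 28 days from the previous one.
- *That ORR is also distorted.* SAP 2.6 says "If any non-palliative cancer therapy is taken while on study any subsequent assessments will be excluded from the BOR determination", which is limited to non-palliative therapy while on study. Losing a responder would also need a confirming scan after the last dose, and IWG responses need no confirmation. This is too remote to claim.

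The 7-21 day scenario reaches 21 + 21 = 42 days after the last dose, past the 37-day contact, so its lower share is partly outside the collection window.

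**Conclusion.** The concern holds in a limited form. For a patient whose PD is first documented after the last dose and whose therapy began later in the same recorded month, the stated rule reverses the true order and replaces a PFS or DOR event by censoring at the last adequate assessment. Among patients with such a PD, later therapy and a day-missing record, roughly 50-85% of PDs would be lost if therapy starts within about one to three weeks. This assumes last-dose days spread evenly over the calendar and that the imputed dates feed the PFS and DOR derivations.

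The number of affected patients is not given and is probably small. One affected patient in a group of 25 moved the mean median by 1.3 weeks or less in the illustrations. The documents therefore do not support a statement that this study's PFS is materially overstated. PFS and DOR are secondary and descriptive, and the neuroblastoma activity rule uses ORR. The rule should still be corrected, because its error runs in the favorable direction and the repair is cheap.

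**What to change.** Add to SAP 5.6.4, under post therapies: for PFS and DOR, if a documented PD falls within the month (or year) left open by a partial therapy start date, impute the start as max(last dose + 1, first of the month or 01JAN, PD date + 1). If PD + 1 falls outside the recorded month (or year), keep the PD as the event. Do not apply this where a known therapy end date precedes the PD. Keep the current rule as a sensitivity analysis.

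In the first example (last dose 06 Mar, PD 20 Mar, therapy recorded as March only), the start becomes 21 Mar instead of 07 Mar and the event on 20 Mar is retained.

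The cost is a short SAP addition and one program condition. The downside is that the outcome helps to set the censoring date, so a PD that truly followed an undated earlier therapy start would count as an event. That error is conservative for a single-arm PFS estimate, and the sensitivity analysis would show its extent.

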5.6.5 Incomplete assessment dates for tumor assessment

All investigation dates (e.g. X-ray, CT scan) must be completed with day, month and year.

If one or more investigation dates are incomplete but other investigation dates are available, the incomplete date(s) are not considered for calculation of the assessment date and assessment date is calculated as the latest of all investigation dates (e.g. X-ray, CT-scan) if the overall lesion response at that assessment is CR/PR/SD/UNK. Otherwise, if overall lesion response is PD, the assessment date is calculated as the earliest date of all investigation dates at that evaluation number. If all measurement dates have no day recorded, the first of the month is used.

If the month is not completed, for any of the investigations, the respective assessment will be considered to be at the date, which is exactly between the previous and the following assessment. If both a previous and following assessments are not available, this assessment will not be used for any calculations. In case of multiple imaging scans performed within an evaluation, if some imaging dates for tumor assessment under the same evaluation for a patient are before as well as after cut-off, the entire evaluation will not be included for analyses based on the pre-specified

cut-off. Hence, only complete tumor assessments (with all imaging dates on or prior to the cut-off) for an evaluation will be included for analyses as determined by the pre-specified cut-off.

5.6.6 Incomplete date for death

All dates must be completed with day, month and year.

Missing month and year will not be imputed. If the day is missing, death will be imputed to the maximum of the full (non-imputed) last contact date (excluding the date of death) and the following:

- Missing day: 1st day of the month and year of death

5.6.7 Last contact date

The last contact date will be derived for patients not known to have died at the analysis cut-off using the last complete date among the following:

Table 5-8 Last contact date data sources

Source data	Conditions
Date of Randomization	No Condition
Last contact date/last date patient was known to be alive from Survival Follow-up page	- Patient status is reported to be alive, lost to follow-up or unknown.
Start/End dates from further antineoplastic therapy	Non-missing medication/procedure term.
Start/End* dates from drug administration record	Non-missing dose. Doses of 0 are allowed.
End of treatment date from end of treatment page	No condition.
- Tumor (RECIST) assessment date - For non-RECIST studies, any specific efficacy assessment date if available	Evaluation is marked as 'done'.
Laboratory/PK collection dates	Sample collection marked as 'done'.
Vital signs date	At least one non-missing parameter value
Performance Status date	Non-missing performance status
Start/End dates of AE	Non-missing verbatim term

- The last contact date is defined as the latest complete date from the above list on or before the data cut-off date. The cut-off date will not be used for last contact date, unless the patient was seen or contacted on that date. No date post cut-off date will be used. Completely imputed dates (e.g. the analysis cut-off date programmatically imputed to replace the missing end date of a dose administration record) will not be used to derive the

last contact date. Partial date imputation is allowed for event (death)/censoring is coming from 'Survival information' eCRF.

5.6.8 Incomplete dates for last dose of study drug

Scenario 1

If the last date of study drug is after the cut-off date or is completely missing and there is no end of treatment eCRF page and no death date the patient should be considered to be on-going and use the cutoff date for the analysis as the last dosing date

Scenario 2

If the last date of study drug is completely or partially missing and there is EITHER an end of treatment eCRF page OR a death date available then imputed last dose date:

= 31DECYYYY, if only Year is available and Year < Year of min (EOT date, death date)

= Last day of the month, if both Year and Month are available, and EITHER:

-- Year = Year of min (EOT date, death date) and Month < the month of min (EOT date, death date) OR,

-- Year < Year of min (EOT date, death date) irrespective of the month

= min (EOT date, death date), for all other cases

5.6.9 Incomplete dates for disease progression prior to start of study drug

If day of PD associated with prior antineoplastic medication is missing then imputed PD date:

= min (midpoint between the end date of the prior antineoplastic medication and the end of the month, start date of LDK, start date of prior medication from the next regimen), if end date of prior antineoplastic medication is in the same month as the PD date,

= min (15th of the month of the PD date, start date of LDK, start date of prior medication from the next regimen), if end date of prior antineoplastic medication is in a month prior to the PD date

= 15th of the month of the PD date, if end date of prior antineoplastic medication is in a month after the PD date.

If both day and month of PD associated with prior antineoplastic medication are missing then imputed PD date:

= min (midpoint between the end date of the prior antineoplastic medication and the end of the year, start date of LDK, start date of prior medication from the next regimen), if end date of prior antineoplastic medication is in the same year as the PD date

= min (July 1 of the year of the PD date, start date of LDK, start date of prior medication from the next regimen), if end date of prior antineoplastic medication is in a year prior to the PD date

= July 1 of the year of the PD date, if end date of prior antineoplastic medication is in a year after the PD date

Completely missing PD dates will not be imputed. The start date of medication from the next regimen is based on the earliest start date of any medication(s) from the next regimen. For the mid-point calculation, if odd days in between, (e.g. last dose of medication is 27 June 2012,

and end of the month is 30 June 2012), then use the next day from the midpoint calculation (e.g. mid-point is 29 June 2012).

